### **Data Analysis**

For the RCT study, data analysis will be performed according to the intention-to-treat principle. Baseline characteristics between the two study arms will be compared by t-test, chi-square or Fisher's exact test as appropriate. The generalized estimating equation (GEE) model will be used to compare the differential changes on the outcomes across the time points T0, T1 and T2 between the two study arms with adjustment for potential confounding variables. Baseline characteristics with p values < 0.25 for between-group difference will be considered as potential confounding variables. GEE model can account for intra-correlated repeated measures data and accommodate missing data caused by incomplete assessments or dropout, provided that the data are missed at random, and thus are particularly suitable for intention-to-treat analysis without the need of imputation for missing data. All statistical analyses will be performed using IBM SPSS 25.0. All statistical tests will be two-sided and a p-value < 0.05 will be considered statistically significant. For the qualitative study, the audio-taped data will be transcribed verbatim. The principal investigator will ensure accuracy of the transcription by cross-checking. Content analysis will be adopted to code the qualitative data on participants' perceptions and acceptability of the technology-based self-care support intervention. The analysis will also seek to understand why and how the study intervention influences patients' health behaviors. The codes will be organized into categories and subcategories, which will be analyzed for emerging themes. The trustworthiness of the qualitative analysis will be enhanced by audio-taping of the interviews, conducting an audit trail, involving two team members to code the qualitative data independently.

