### Study participants

Adults will be eligible to join the study if they are: 1) living in the community, 2) owning a smartphone with internet access, 3) communicable in Cantonese, 4) able to type in Chinese or English, and 5) with a confirmed diagnosis of CAD. Individuals will be excluded if they have: 1) enrolled to a structured center-based or home-based cardiac rehabilitation programme in the past year, 2) known psychiatric problems, 3) impaired cognitive functioning (i.e. Abbreviated Mental Test  $\leq 6$ ), and 4) terminal disease with life expectancy  $< 1$  year.

For the RCT, the sample size is determined on the basis of a systematic review that identified small to medium effect sizes (0.42–0.66) of information and communication technology-based cardiac rehabilitation on health behaviors among patients with CAD. This study will conservatively assume an effect size as 0.4. The power analysis software PASS 14 (NCSS, Kaysville, UT) estimated that a sample size of 100 subjects per study group would give the proposed two-arm randomized controlled trial 80% power at a two-sided 5% level of significance to detect an effect size of 0.4 on the primary outcome between the control and intervention groups at the post-intervention time point. After allowing for a potential dropout rate of up to 25%, 268 subjects (i.e. 134/group). For the qualitative phase, a criterion sampling of 30 participants who have received the i-CARE program will be invited to join on the basis of their post-intervention changes in the primary outcome, with 10 participants from each

category (low, medium and high percentile). Maximum variations in the participants' sociodemographic and clinical characteristics will also be considered in the sampling procedure to ensure a wider range of data.

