#### Randomization and blinding

After collecting baseline data, the research nurse will randomly allocate patients into the intervention or control group. Block randomization (block size: 8, 10, or 12) will be used to ensure even participant distribution between the two groups. The block size and respective study group allocation sequence will be determined using a computer-generated sequence. Chronologically recruited patients will be allocated to the study groups by the nurse according to this computer-generated sequence. Participants allocated to the intervention group will receive the i-CARE intervention, while those allocated to the control group will continue to receive conventional care as arranged by the hospital. An independent research assistant who is blinded to study group allocations will collect post-intervention data.

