## **Data collection procedure**

After obtaining the approval from the respective ethics research committees, the research nurse will recruit eligible participants from the cardiac clinics and wards of two regional hospitals in Hong Kong. The local PI will identify potential subjects from the admission record and follow-up list of the cardiac ward and clinics respectively, and refer them to the research nurse. The research nurse will screen their eligibility according to the predefined criteria. All the eligible patients will be invited to participate. He/she will introduce the study to potential participants verbally, supplemented with a written information sheet. After obtaining the participants'

written informed consent, the nurse will collect socio-demographic and clinical data through patient's self-report and medical record review, while the nurse will assist participants to complete the SC-CHDI, SAQ and MacNew through a secured online platform Qualtrics. The physiological, anthropometric and biomarkers will be collected according to the standard protocol. The research nurse will then allocate the participants into intervention or control group by block randomization, to receive the i-CARE intervention or usual care, respectively. The post-intervention data will be collected through the mobile application, a message will be popped up to remind the participants at 3 and 6 months thereafter. A trained research assistant who has no knowledge of the group allocation, will be responsible for collecting the post-intervention physiological, anthropometric and biomarkers. A subsample of the participants will be invited to participate in the qualitative phase. Semi-structured interviews will be conducted by the principal investigator with an interview guide, which includes open-ended questions to enquire about their engagement experience in the intervention.

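### The trial is sized for a between-arm difference at the post-intervention visit, but the planned GEE compares change from T0 without securing adjustment for the T0 score: a cheap gain in alignment and efficiency

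*Combined protocol and SAP*

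**What the plan says.** Study participants gives the sizing: 100 per group, two-sided 5%, 80% power "to detect an effect size of 0.4 on the primary outcome between the control and intervention groups at the post-intervention time point". Allowing for up to 25% dropout, this becomes 134 per group, 268 in all. No SD, correlation or repeated-measures term is stated.

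Data Analysis gives the test: a GEE "will be used to compare the differential changes on the outcomes across the time points T0, T1 and T2 between the two study arms", adjusted for potential confounders. These are the baseline characteristics whose between-group p value is below 0.25. The section presents the model as coping with incomplete follow-up "provided that the data are missed at random" and "thus are particularly suitable for intention-to-treat analysis without the need of imputation for missing data". It contains no model equation, no working correlation structure, no primary time coefficient and no statement on how the T0 score enters.

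The T0 score is available before allocation. Randomization and blinding says "After collecting baseline data, the research nurse will randomly allocate patients into the intervention or control group", and Data collection procedure says "the nurse will assist participants to complete the SC-CHDI, SAQ and MacNew through a secured online platform Qualtrics" as part of that baseline step. For follow-up, "a message will be popped up to remind the participants at 3 and 6 months thereafter". T0, T1 and T2 are not defined. Here T0 is read as the pre-allocation assessment, T1 as the 3-month visit at the end of the 12-week intervention, and T2 as the 6-month visit.

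**The concern.** The two sections describe different contrasts. The sizing compares arm means at one visit, and its power needs no correlation. A differential change with T0 among the response times is a group-by-time term, and the variance of a change depends on rho. The stated 80% therefore does not carry over to the planned test without a figure that the documents do not give.

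The p < 0.25 screen does not close the gap. Whether the T0 score enters depends on chance imbalance. Even if it enters, a main-effect covariate shifts all of a participant's visits equally and so largely cancels out of a change. What is at stake is precision the trial could have at no cost, and a clear statement of which estimate answers the primary question.

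**Working it through.** **1. The plan's own figure.** With effect 0.4, SD 1 and two-sided 5%:

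- n per arm = 2(1.960 + 0.842)² / 0.4² = 98.1, so 99 (normal); the t-test version gives 99.08, so 100.
- Power at 100 per arm: Φ(0.4/√(2/100) − 1.960) = Φ(0.868) = 80.7%; with the t distribution, 80.4%.
- Dropout: 100/0.75 = 133.3, so 134 per arm and 268 in total.

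The stated sizes reproduce, as a two-sample comparison at one visit.

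**2. Assumptions for the planned contrast.** Rho is not given, so a range is shown. The 0.4 is in post-intervention SDs; SDs and correlations are equal across visits; per arm, 134 have T0 and 100 have follow-up (the full 25% loss, all before T1); dropout is completely at random; the working correlation is exchangeable.

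**3. Variance per arm** (the difference between arms has twice this):

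- Group-by-T1 change, T0 means free: v = (1 − ρ²)/100 + (1 − ρ)²/134
- T0-adjusted difference at T1: v = (1 − ρ²)/100

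Power = Φ(0.4/√(2v) − 1.960). At ρ = 0.3 the change contrast has v = 0.00910 + 0.00366 = 0.01276, so power = Φ(2.504 − 1.960) = 70.7%. The adjusted contrast has v = 0.00910, so power = Φ(2.965 − 1.960) = 84.3%.

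| ρ | Group-by-T1 change | T0-adjusted T1 difference | Variance ratio |
|---|---|---|---|
| 0 | 57.2% | 80.7% | 1.75 |
| 0.3 | 70.7% | 84.3% | 1.40 |
| 0.4 | 76.6% | 87.0% | 1.32 |
| 0.5 | 83.2% | 90.4% | 1.25 |
| 0.6 | 90.1% | 94.2% | 1.19 |

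**4. Where the change contrast reaches 80%.** This needs v = (0.4/2.802)²/2 = 0.01019.

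- 100 followed: ρ = 0.45.
- 121 followed (about 10% loss): (1 − ρ²)/121 + (1 − ρ)²/134 = 0.01019, so ρ is about 0.36.
- No loss: 2(1 − ρ)/134 = 0.01019, so ρ is about 0.32.
- 100 followed, working independence: v = 1/100 + 1/134 − 2ρ/134, so ρ is about 0.49.

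**5. Simulation of the GEE** (exchangeable working correlation, robust SEs, dropout completely at random, 3,000 trials per setting, effect 0.4 at both follow-ups). At ρ 0.3/0.4/0.5/0.6, group-by-T1 power was 71.2/78.8/84.2/89.6%. With arm means constrained equal at T0 it was 83.9/88.3/90.7/93.9%. Type I error of the planned contrast was 4.5% at ρ 0.3 and 5.4% at ρ 0.5. Adding a main-effect covariate left the group-by-T1 estimate unchanged with complete data, and changed its mean SE by no more than 2% with dropout.

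**6. Constraining T0 means needs a working correlation.** Under working independence the constrained estimate is the raw T1 difference: v = 1/100 and power 80.7% at every ρ. The planned change contrast under independence gives 69.9/75.1/80.7/86.6% at ρ 0.3/0.4/0.5/0.6, so above 0.5 the constraint would do worse than the plan.

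**The case against.** Change from baseline and baseline-adjusted follow-up are both valid analyses in a randomised trial, so choosing one is not an error. That stands.

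A reader might infer that the trial is underpowered. The documents do not support that. Rho is not given, and above about 0.45 the planned contrast exceeds 80% even with the full 25% loss. That loss is the plan's upper limit, and the threshold drops to about 0.36 or 0.32 with less. It also depends on which test is primary. With 0.4 sustained at both follow-ups and 100 followed, a joint two-degree-of-freedom test reaches 80% at rho of about 0.38 and an averaged follow-up effect at about 0.22. The SD unit of the 0.4 is not stated either. In SD-of-change units, a complete-case change contrast with 100 per arm has 80% at any rho and the power concern goes away. The sizing text, which refers to the post-intervention time point, favours post-intervention SDs but does not settle it.

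A reader might also infer that the planned test is biased. Nothing here shows that: with non-informative dropout the contrast is valid, though the simulation covers only dropout completely at random.

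Finally, the model is inferred from a sentence, and confounder adjustment might bring in the T0 score. It might, but the rule does not ensure it, and a main effect would leave the group-by-time contrast essentially unchanged. In any SD unit, the sizing and the analysis still name different contrasts.

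**Conclusion.** The point holds as a minor-to-moderate improvement in alignment and efficiency. The sample-size arithmetic is correct, but it belongs to a contrast that the Data Analysis section does not name. Under the assumptions in the working, not securing T0 adjustment costs about 14 percentage points of power at rho 0.3 and 4 at rho 0.6, with a variance ratio from 1.40 to 1.19. The T0-adjusted T1 difference keeps the planned 80% at any non-negative rho under those assumptions; the change contrast does so only from about 0.45 upwards. The size of the gain rests on an unknown rho, on 0.4 being in post-intervention SDs, and on the natural reading of a model with no written equation. Confidence is medium.

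**What to change.** In Data Analysis, name the T0-adjusted between-arm difference at T1 (the 3-month, end-of-intervention visit) as the primary contrast, and define T0, T1 and T2. Fit T1 and T2 as responses, with arm, visit, arm-by-visit, the T0 score and T0-by-visit. Prespecify the T0 score as a covariate regardless of the p < 0.25 screen. In Study participants, state the SD in which 0.4 is expressed.

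The small downside is that participants with no follow-up score leave the model; in the planned GEE they contribute only T0 values. If keeping every randomised participant in the model matters, the alternative is to keep T0 as a response with arm means constrained equal at T0. Use that only with a prespecified non-independence working correlation (exchangeable or unstructured) and robust SEs, since under working independence the constraint gives no T0 adjustment. A badly matched working structure costs little: with an exchangeable structure and true T0–T1, T0–T2 and T1–T2 correlations of 0.1, 0.1 and 0.7, constrained power is 79.6%.

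The cost is wording only. The T0 score is already collected before allocation, so no new data, visits or participants are needed.

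### GEE covariates are picked by a p<0.25 test of baseline difference between randomised arms, which selects on chance and ignores prognostic value; a short fixed list should replace the rule

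*Combined protocol and SAP*

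**What the plan says.** Under Data Analysis, the arms are first tested against each other at baseline: "Baseline characteristics between the two study arms will be compared by t-test, chi-square or Fisher's exact test as appropriate". The results of those tests decide the adjustment: "Baseline characteristics with p values < 0.25 for between-group difference will be considered as potential confounding variables". The main model is a GEE, whose stated task is to "compare the differential changes on the outcomes across the time points T0, T1 and T2 between the two study arms". So T0 is one of the repeated responses, and the treatment effect is an arm-by-time contrast. The screened variables come in through a single phrase, "with adjustment for potential confounding variables".

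Allocation is random: "Block randomization (block size: 8, 10, or 12) will be used to ensure even participant distribution between the two groups" (Randomization and blinding). No stratification factor is named.

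The plan gives no covariate list, does not make prognostic value a criterion, and does not say whether covariates enter as main effects or with time interactions. The stated operating characteristics are "80% power at a two-sided 5% level of significance to detect an effect size of 0.4 on the primary outcome" (Study participants) and, for the analysis, "All statistical tests will be two-sided and a p-value < 0.05 will be considered statistically significant". The sample size is a plain two-group comparison that claims no gain from covariates.

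**The concern.** Under random allocation, a baseline p-value measures only how uneven the draw happened to be. It says nothing about whether the characteristic predicts self-care, so a strong predictor and an irrelevant variable have the same chance of entering the model. A screen of this kind belongs to observational work, where imbalance can be systematic.

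Two things are at stake. The primary model cannot be written down until the arms have been compared, and it depends on which characteristics are put through the screen. The plan also promises adjustment for confounding by a route that, depending on the form of the model, either forgoes available power or has almost no effect on the tested contrast.

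**Working it through.** **Inputs from the documents.** Screening threshold 0.25; two-sided 5%; effect size 0.4 (SD 1); 100 evaluable per arm; 25% dropout; 134 per arm recruited.

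**Assumptions, because the documents give no figure.** Number of independent baseline characteristics K = 5 to 20; correlation r of one covariate with the T1 score = 0.3 or 0.5; within-patient correlation 0.5 in the GEE runs.

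**1. The plan's own figures.** n per arm = 2(1.96 + 0.8416)²/0.4² = 98.1, so 99 (99.08 with the t-distribution, so 100). Standard error with 100 per arm = √(2/100) = 0.1414; power = Φ(0.4/0.1414 − 1.96) = 0.807. Recruitment = 100/0.75 = 133.3, so 134 per arm and 268 in total. The plan's numbers reproduce.

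**2. What the screen selects.** Each characteristic passes with probability 0.25 and is omitted with probability 0.75, whatever its prognostic strength. Expected number selected = 0.25K; P(at least one) = 1 − 0.75^K.

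| K | expected selected | P(at least one) |
|---|---|---|
| 5 | 1.25 | 76% |
| 10 | 2.5 | 94% |
| 20 | 5 | 99.7% |

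**3. Case (a): covariates act on the post-baseline contrast.** Take a T1 comparison with 100 per arm and one covariate.

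- Fixed adjustment: SE = 0.1414√(1 − r²), which is 0.1349 for r = 0.3 and 0.1225 for r = 0.5. Power = Φ(0.4/SE − 1.96) = 0.84 and 0.90.
- With the screen, the covariate is omitted when its standardised imbalance is below c = 1.150. Given that, the variance of the imbalance is 1 − 2cφ(c)/0.75 = 1 − 2(1.150)(0.2059)/0.75 = 0.37 of its unconditional value. The unadjusted estimate then varies less than its standard error says, by the factor √(1 − r² + 0.37r²) = 0.971 (r = 0.3) or 0.918 (r = 0.5).
- Error when omitted ≈ 2Φ(−1.96/0.971) = 4.4%, or 2Φ(−1.96/0.918) = 3.3%. Overall ≈ 0.75 × 4.4% + 0.25 × 5% = 4.5%, or 0.75 × 3.3% + 0.25 × 5% = 3.7%.
- Power when omitted ≈ Φ((0.4 − 1.96 × 0.1414)/(0.1414 × 0.971)) = 0.81, or 0.83 with 0.918. Overall ≈ 0.75 × 0.81 + 0.25 × 0.84 = 0.82, or 0.75 × 0.83 + 0.25 × 0.90 = 0.85.

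Simulated trials agree with this approximation:

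| r | error, screen | error, fixed | power, screen | power, fixed |
|---|---|---|---|---|
| 0.3 | 4.4% | 4.9% | 82% | 85% |
| 0.5 | 3.6% | 4.8% | 84% | 90% |

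With ten characteristics screened and two of them prognostic (correlations 0.3 and 0.2, 0.5 and 0.3, 0.7 and 0.3), simulated error was 4.2%, 3.5% and 2.0%. Power was 81%, 84% and 88% with the screen, against 85%, 93% and 99% with the two covariates fixed.

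If T0 stays a response and covariates get time interactions, the same mechanism applies, but r is then the correlation with change from T0 rather than with the T1 score.

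**4. Case (b): covariates enter the GEE as main effects only.** A term that is constant over time cancels from a difference in changes. In simulations with complete data (exchangeable working correlation, robust standard errors), the arm-by-T1 estimate was the same whether screened, fixed or unadjusted, to about 1e-14, with power 0.79 in all three. With 134 per arm and about 25% covariate-dependent dropout, error was 5.4% screened, 5.3% fixed and 5.2% unadjusted, and power was 0.83 in all three. The estimate itself moved by 0.012 to 0.031 SD on average across sets of runs; the largest shift in any single run was 0.10 SD.

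**The case against.** The best defence is that the plan's guarantees hold. The design states 5% error and 80% power for an unadjusted comparison, and under the mechanically applied rule neither is broken. A reader might infer that the stated error rate and power are not delivered; the documents and the arithmetic do not support that. This defence stands: what is lost is optional extra power.

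The strongest predictor is probably the outcome's own baseline value, and T0 is in the GEE whatever the screen does. This also stands, and it limits the 75% omission figure to other characteristics. It also answers the inference that imbalance is left wholly uncorrected: a covariate effect that is constant over time cancels in the change contrast, so only an effect on change remains.

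The losses in case (a) and the inertness in case (b) belong to different model forms and must not be added together. It would also be too strong to say that a main-effect covariate cannot alter the contrast. That is exact only with complete data, and the plan allows for up to 25% dropout.

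Finally, a reader might infer outcome-driven model choice. The screen uses baseline data only, its threshold is written in advance, and nothing says outcomes inform it. The wording does leave room for discretion over which passing variables to use, but the documents give no basis for sizing that.

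None of this defends the rule itself. Under neither form of adjustment does it achieve the purpose stated for it.

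**Conclusion.** The concern holds in a limited form. The rule selects covariates on chance imbalance, omits any given prognostic characteristic other than the T0 outcome about three times in four, and leaves the primary model unfixed until the arms are compared.

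Its cost depends on a choice the plan does not state. In case (a), with one covariate at an assumed correlation of 0.3 to 0.5, a nominal 5% test runs at about 4.4% to 3.6% and forgoes about 3 to 6 points of power (82% against 85%; 84% against 90%). With two prognostic covariates the loss is about 4 to 11 points. In case (b) the adjustment is inert with complete data and nearly so with dropout.

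These sizes rest on assumed correlations, independent characteristics and mechanical use of the threshold. The trial's validity is not in question. This is an inexpensive improvement that should be made.

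**What to change.** 1. Delete the p<0.25 rule and the between-arm significance tests at baseline. Describe baseline characteristics by arm only.
2. Before any T1 data are seen, write into the plan a short list of covariates expected to predict the outcome. Draw them from the socio-demographic and clinical data collected before allocation (Data collection procedure). That section does not itemise these data, so confirm that each chosen variable is recorded.
3. Adjust for the list whatever the observed balance.
4. State the form: covariate-by-time terms in the T0/T1/T2 GEE, or a T1/T2-only model. In the latter, the T0 value of the outcome moves from response to covariate and belongs on the list.

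The cost is a wording change. No new visits or patients are needed, and no new data if the list is confined to what is already recorded. The team must agree the list in advance, and a few degrees of freedom are used.

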The chat room will serve as a platform to facilitate the nurse to provide coaching to motivate and facilitate behavioral changes of the participants. The nurse will review the self-monitoring data and keep track on the progress of goal attainment of each participant. He/she will initiate chatting with the participants in this platform weekly, to identify any problems that the participants encountered in their daily practice of self-care behaviors, and will explore the underlying barriers, then advise resolving methods to minimize the barriers and improve adherence. Health counselling and advice given will be documented to guide subsequent communication. Throughout the process, the nurse will adopt therapeutic communication skills, and a supportive and non-judgmental attitude. The participants can also initiate the communication with the nurse in the chat room regarding disease management. The nurse will offer advice and counselling accordingly during office hours. An automatic system-generated message will pop up to remind the participants to seek urgent medical care for newly onset symptoms that may suggestive of disease exacerbation or deterioration.

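### The plan claims that GEE under missing at random makes imputation unnecessary; this is not true in general, and the working correlation on which it depends is not named

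*Combined protocol and SAP*

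**What the plan says.** The Data Analysis section uses GEE to "compare the differential changes on the outcomes across the time points T0, T1 and T2 between the two study arms". It justifies the choice in two steps. First, "GEE model can account for intra-correlated repeated measures data" and can "accommodate missing data caused by incomplete assessments or dropout, provided that the data are missed at random". Second, such models therefore "are particularly suitable for intention-to-treat analysis without the need of imputation for missing data".

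This is the whole missing-data strategy. The plan names no working correlation, weighting, multiple imputation, likelihood-based model or missing-data sensitivity analysis. Covariates are chosen by a baseline screen: "Baseline characteristics with p values < 0.25 for between-group difference will be considered as potential confounding variables".

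The sample size paragraph (Study participants) sets the scale of missing data that the investigators are prepared for: "After allowing for a potential dropout rate of up to 25" per cent. The same paragraph powers the trial at the post-intervention time point, taken here as T1 (3 months).

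**The concern.** Under missing at random (MAR), dropout may depend on anything already observed, including earlier values of the outcome. Ordinary GEE is not protected against that form of dropout. Because T0 enters as a response and not as a covariate, even dropout that depends only on the baseline score falls outside the guarantee. Adjusting for baseline characteristics that pass the screen covers only dropout explained by those characteristics.

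With complete data the working correlation mainly affects efficiency. With outcome-related dropout it also decides whether the estimate is approximately right, so leaving it open while claiming validity under MAR is more than a missing detail.

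Dropout that differs by arm is plausible here. Weekly nurse contact belongs to i-CARE only ("He/she will initiate chatting with the participants in this platform weekly"), controls receive usual care, and "The post-intervention data will be collected through the mobile application", while account registration is described only in the i-CARE orientation session. At stake is the between-arm effect on the self-reported primary outcome, which could be over- or understated.

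**Working it through.** **Plan's own figure.** n per group = 2(1.960 + 0.842)²/0.4² = 98.1, so 99; the t-test version gives 99.08, so 100. Dropout: 100/(1 − 0.25) = 133.3, so 134 per group and 268 in total. This reproduces and is not in dispute.

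**Why the working correlation matters.** Take one arm, T0 complete, and dropout before T1 that depends on T0. Let ρ be the true correlation, ρw the working correlation, and m the excess of the mean T0 score (in SD) among those retained over the mean of all. With equal variances and two visits, the GEE estimate of the T1 mean is the retained T1 mean minus ρw × m. The retained T1 mean is itself too high by ρ × m. Hence

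bias at T1 in that arm = (ρ − ρw) × m.

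Independence (ρw = 0) leaves ρ × m; a correct ρw leaves nothing. The between-arm bias is the difference of this quantity between arms, so it cancels when slope and rate are equal.

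**Size of m.** If the log-odds of dropout rise by s per SD lower score, T0 is normal, p is an individual's dropout probability and q is its mean, then m = s × E[p(1 − p)]/(1 − q), which is at most s × q. A total of 25% over two equal intervals gives q = 1 − √0.75 = 0.134. With s = 1 and ρ = 0.5, the T1 bias under independence is at most 0.5 × 0.134 = 0.067. With s = 0.5 it is at most 0.034.

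**Assumed inputs.** The documents give no correlation, slope or arm-specific dropout rate. The illustration assumes a true effect of 0.40 SD at T1 and T2, exchangeable correlation 0.5, monotone dropout that depends on the previous score, 25% in total by T2 unless stated, and the contrast as differential change from T0. The 25% is the plan's upper allowance, not an expected rate.

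**Large-sample estimates, independence working correlation (true value 0.40)**

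| Dropout pattern | T1 | T2 |
|---|---|---|
| A: low scorers leave, i-CARE only, slope 1 | 0.46–0.47 | 0.52 |
| B: low scorers leave, control only, slope 1 | 0.34 | 0.29 |
| B, milder: slope 0.5 | 0.37 | 0.34 |
| C: slope 1 in both arms, 35% control, 15% i-CARE | 0.35 | 0.31 |
| D: slope 1 in both arms, 15% control, 35% i-CARE | 0.45–0.46 | 0.49–0.50 |
| E: equal slopes and equal rates | 0.40 | 0.40 |

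The T1 values for A and B respect the hand bound (0.40 ± 0.067 = 0.333 to 0.467). At correlations of 0.3 and 0.7, T2 is 0.47 and 0.56 in A, and 0.33 and 0.24 in B.

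**Other working structures, A to E**

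- Exchangeable: about 0.40 when that structure is true, and about 0.38 to 0.42 when the truth is autoregressive.
- Unstructured: about 0.39 to 0.41.
- If the two arms have opposite mechanisms, a more extreme assumption, exchangeable ranges from 0.37 to 0.43 at T1 and unstructured from 0.38 to 0.42.

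**Error rates (3,000 simulated trials of 134 per arm; Monte Carlo standard error about 0.4 points at 5%).** Under independence, type I error at T1 is 7.6%, 6.5%, 6.4% and 6.6% in A to D; at T2 it is 13.5%, 13.8%, 9.6% and 9.8%. Power in B, independence against unstructured, is 73% against 87% at T1 and 53% against 83% at T2. Of the 30-point gap at T2, about 4 points are lost efficiency, because independence has 79% in the unbiased pattern E.

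**The case against.** The strongest reply is that every large figure above needs an independence working correlation, which the plan does not choose. The plan invokes GEE partly because it accounts for correlated repeated measures, which sits more naturally with a modelled correlation. With an ordinary exchangeable structure the bias is about 0.02 SD in A to E, which is small beside an effect of 0.40. This stands, and it limits the finding. It does not repair the plan, because no structure is pre-specified and the choice could be made after the data are seen.

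The patterns are also strong. A and B put a slope of 1 in one arm and none in the other, and C and D exceed 25% in one arm. A slope of 0.5 in control only gives 0.37 and 0.34, with T2 type I error of 6.9%; a 30%/20% split with slope 1 gives 0.38 and 0.35, with 6.0%. The worst figures are at T2, whereas the trial is powered at the post-intervention visit. These points stand too.

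The plausibility argument is partial. Collection through the app bears on the questionnaires; a blinded assistant collects the physiological measures. Nurse contact may change how many drop out, but bias also needs dropout to be related to scores.

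A reader might infer that the planned analysis will be biased, or that power will fall from 83% to 53%. The documents do not support that: they give no dropout pattern, no direction and no working correlation.

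**Conclusion.** The statement that GEE under MAR removes the need for imputation is wrong as a general rule, and the choice that decides whether it is approximately right is missing. That conclusion rests on the properties of unweighted GEE and on the three visits all being modelled outcomes; it needs no simulation.

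The size of any bias is conditional. Material bias in the between-arm effect needs both an independence (or badly fitting) working correlation and score-related dropout that differs between arms in strength or rate. Under the assumptions shown, independence moves a true 0.40 SD by about 0.06 at T1 and about 0.12 at T2 in either direction when the slope is 1 in one arm. A reasonable working correlation leaves about 0.02 SD, and equal dropout mechanisms and rates leave essentially none. The point should be corrected because the correction is cheap, not because harm has been shown.

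**What to change.** - Delete the statement that GEE under MAR makes imputation unnecessary.
- Pre-specify one primary model for the continuous outcomes: a linear mixed model for repeated measures fitted by REML, with T0, T1 and T2 as responses, group-by-visit fixed effects and an unstructured covariance. It is valid under MAR when correctly specified. Three visits need only three correlations, which 268 participants can support.
- Keep GEE with an unstructured working correlation and robust standard errors as a sensitivity analysis. Multiple imputation or an analysis for data not missing at random is an optional addition.

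This covers the continuous outcomes only; cardiovascular events and mortality are outside it. The cost is a change of wording and slightly more analysis work. No new data are needed, and the sample size stays at 134 per group.
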